### *Secondary Outcome Measures*

- Substance Use
  - Drug Abuse Screening Test (DAST)

### *Other Self-Reported Measures*

- Demographics
- Brief Symptom Inventory-18 (BSI-18)
- Self-Efficacy VAS for Alcohol, Drugs, Adherence, Sex Risk, and Doctor's Visits
- Patient Satisfaction
  - Participant Experience of Motivational Interviewing (CEMI) Scale
  - Patient's Experience with the Provider

## **Data Collection**

All baseline and follow-up assessments are administered at the study sites. Baseline data collection was completed within the same day, and no later than 7 days after the screener is completed. All follow-up data collections (3M, 6M, 9M, 12M, 15M, and 18M) could be collected up to 14 days prior/post to their follow-up target date and up to 28 days post their follow-up target date.

## **Compensation**

To compensate participants for their time and efforts in taking part in the PLUS trial, gift cards and metro cards were given out at each assessment and therapy visit, respectively, in two different denominations for participant compensation:

\$25 Gift cards- which will be dispersed during study assessments (BL, 3M, 6M, 9M, 12M, 15M, and 18M)

\$10 Metro cards- which will be dispersed during therapy visits (Sessions 1-6)

Throughout the course of the PLUS trial, a study participant may receive \$235 for their participation.

## **Selection of No Treatment control patients**

The EMRs of randomly selected patients who belonged to the TAU site and were not enrolled in the PLUS trial were matched on key patient characteristics for comparisons with EMRs of patients in the PLUS intervention and Waitlist control conditions. This matched cohort of patients received care at a fourth clinic that did not receive any intervention (i.e., PLUS or eTAU) and was considered as a natural history comparison group. We generated a pool of patient records from which to randomly select the TAU matched cohort of patients ( $n = 120$ ). We included patient records of patients with an HIV diagnosis who had at least 1 primary care visit at the TAU clinic, received ART, and had a viral load (VL)  $>200$  copies/mL during the PLUS enrollment period from March 26, 2015 to March 16, 2017. EMRs of 20 patients who were enrolled in PLUS and possibly transferred to receive HIV care at the TAU clinic during the study period were excluded. Additionally, records of 9 patients with only one primary care visit and no follow-up visits during the study period were excluded from the pool of patient records.

Case control matching using the pool of patients meeting the criteria described above allowed us to randomly select the TAU cohort of 120 patients while matching as closely as possible to patients enrolled in the trial on key variables: age group (with ranges 18-29, 30-39, 40-49, and 50 or older), racial and ethnic identity (Black, Hispanic/Latinx, White, Asian/Pacific Island, Other/Multiracial), and gender (recorded as male or female). Additionally, we matched on indicators of substance misuse based on EMRs of trial participants using documentation of substance use problems or ICD-10 diagnostic codes, such as documentation of alcohol abuse or dependence, having had a substance use diagnosis, or any indication of substance misuse during the study period. EMRs were then extracted for the TAU cohort of patients similar to the records

for the trial participants. A de-identified dataset was generated linking all patient EMRs to an unique study ID number with the following variables: demographic variables, HIV diagnosis, HIV clinical outcomes, ARV regimen, ICD-10 diagnoses of AIDS defining illness, substance use disorders, psychiatric disorders, non-AIDS defining infections (bacterial pneumonia, cellulitis, sepsis), cardiovascular, gastrointestinal, liver, kidney, pulmonary, endocrine, immune, and oncologic diseases, as well as sexually transmitted infections. In addition, records about services received and type of outpatient clinic visits were extracted, such as whether the visit was an HIV primary care visit, a specialty or non-HIV primary care visit type (dentist, OB/GYN, hematology), mental health visit, and substance use visit.

### **Data Analysis Plan**

To assess the effectiveness of our randomization procedure, we used chi-square tests and ANOVAs to investigate the equivalence of possible cofounders across each of the PLUS-enrolled four site/conditions at baseline. Specifically, we examined proportional differences across demographic characteristics (race and ethnicity, sexual and gender identity, and education), and mean differences across age and baseline outcome values (alcohol severity, drug use severity, medication adherence, viral load, and CD4). Where cell sizes were too small ( $n < 5$ ) to permit chi-square tests, we utilized a Fisher's exact test, at  $p < .05$ . The matching of the No Treatment control group ( $N = 120$ ) was assessed by bivariate comparisons with the entire PLUS-enrolled sample ( $N = 174$ ) on the available variables of age, race and ethnicity, and gender.

We also conducted analyses to test for the presence of differential attrition between conditions and sites where appropriate. First, we conducted chi-square analyses to test for differential attrition by site and study arm at each follow-up. We also tested for differential attrition at each follow-up across site, as well as several demographic characteristics (race and ethnicity, sexual and gender identity, and education). Finally, we conducted a series of point-biserial correlations to examine attrition at each wave by age and baseline outcome values (alcohol severity, drug use severity, medication adherence, viral load, and CD4).

Outcome analyses were conducted using piece-wise longitudinal growth curve models, adjusting for baseline scores on the corresponding outcome and, for the models predicting medication adherence, AUDIT, and DAST, we also adjusted for gender identity and sexual orientation, whereas for the models predicting viral load and CD4 we adjusted for gender (male, female) as sexual identity was not indicated in the EMR records for the matched cohort. For the

DAST model, DAST was treated as a count variable having a negative binomial distribution. The latent intercept represented the initial 3-month follow-up time point. Slope 1 quantified linear change across the 3-, 6-, 9- and 12-month follow-ups. Where possible for outcomes variables extracted from EMR (i.e., CD4 count and viral load), Slope 2 quantified changes in trajectory at the 15- and 18-month follow-up corresponding to the point at which the waitlist control condition received the intervention. The fixed effect of clinic and condition was entered as a 4-category predictor that was dummy-coded. For viral load and CD4 models – where data were taken from EMR records – the EMR cohort control participants were included as an additional subgroup and served as the referent category.

All models were estimated using full-information maximum likelihood estimation in MPlus Version 8.0. Good model fit was assumed when the  $\chi^2/df$  ratio was 3 or less, root-mean square error of approximation (RMSEA)  $\leq 0.05$ , Tucker-Lewis fit index (TLI)  $> 0.95$ , and comparative fit index (CFI)  $> 0.95$ .

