## **Trial Design**

This study utilized a CET design to evaluate the effectiveness of the PLUS intervention components against a waitlist condition, and for VL and CD4, against a No-Treatment control group. Four sites were distributed across three study conditions in a quasi-experimental design. Two sites (Sites 1 and 2) implemented immediate treatment (Condition 1). Immediately after baseline, participants were offered the PLUS intervention. Participants then completed follow-up assessments at 3, 6, 9, 12, 15 and 18 months post-baseline. Site 3 implemented both the waitlist condition (Condition 2) from March 26, 2015 to October 31, 2016, and an immediate condition. Due to challenges in participant accrual, this site shifted to enrolling participants in the immediate intervention condition from November 1, 2016 through the end of the study. Participants in the waitlist condition received the intervention following completion of their 12-month follow-up. Site 4 is the no-Treatment Control EMR Group.

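### The analysis plan describes its baseline tests as a check on randomisation, but allocation was by clinic and enrolment date; the outcome models also leave out age, race/ethnicity and education, which the plan tests as possible confounders

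*Combined protocol and SAP*

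**What the plan says.** Trial Design describes the allocation openly: "Four sites were distributed across three study conditions in a quasi-experimental design". Sites 1 and 2 gave PLUS immediately. Site 3 enrolled to a waitlist from 26 March 2015 to 31 October 2016; then, because accrual was difficult, "this site shifted to enrolling participants in the immediate intervention condition from November 1, 2016". Site 4 supplied untreated medical-record (EMR) controls. The stated purpose is to "evaluate the effectiveness of the PLUS intervention components against a waitlist condition, and for VL and CD4, against a No-Treatment control group".

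The Data Analysis Plan introduces its baseline tests differently: "To assess the effectiveness of our randomization procedure, we used chi-square tests and ANOVAs to investigate the equivalence of possible cofounders". The tests run across the four enrolled site/condition groups. On content, "we examined proportional differences across demographic characteristics (race and ethnicity, sexual and gender identity, and education), and mean differences across age" and baseline outcome values.

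On the models, "The fixed effect of clinic and condition was entered as a 4-category predictor that was dummy-coded". For viral load and CD4, "the EMR cohort control participants were included as an additional subgroup and served as the referent category". Every model adjusts for the baseline value of its own outcome. The adherence, AUDIT and DAST models add gender identity and sexual orientation; the viral load and CD4 models add gender only. Where EMR data allow, Slope 2 covers months 15 and 18, "corresponding to the point at which the waitlist control condition received the intervention".

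Under Selection of No Treatment control patients, 120 Site 4 records were matched to enrolled patients on age group, race/ethnicity, gender and indicators of substance misuse.

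**The concern.** The two sections disagree on how the comparison groups were formed. Under randomisation, baseline differences are chance, and a standard error covers them. Under allocation by clinic and date, differences can be systematic, and a baseline test neither rules them out nor corrects for them. A reader who takes the analysis section at its word may read the group contrasts as randomised effects.

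The covariate list adds to this. The plan names age, race/ethnicity and education among its possible confounders and tests them, then leaves them out of the models without a reason. Missing EMR data is given as the reason only for leaving sexual identity out of the viral load and CD4 models. For AUDIT and self-reported adherence, both primary, the waitlist is the only comparator, so the Site 4 matching gives no help there.

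**Working it through.** The plan gives no sample-size or bias figure to reproduce. The check has three parts.

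**1. Is anything randomised?** The only random step is the drawing of Site 4 records. That is sampling, not allocation. The randomisation clause cannot refer to it, because the tests it introduces compare the enrolled groups.

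**2. What does each contrast differ in, besides PLUS?**

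| Contrast | Also differs in |
|---|---|
| Site 1 or 2 immediate vs Site 3 waitlist | Clinic |
| Any enrolled group vs Site 4 (viral load, CD4) | Clinic |
| Site 3 immediate vs Site 3 waitlist | Calendar period |

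Within Site 3, the design matrix with intercept, condition and period has rank 2 of 3, so PLUS and period cannot be separated there. Inclusion Criteria also reports an undated later widening to illicit drug use, which could change case mix between the two Site 3 periods. No between-group contrast avoids both problems.

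Slope 2 is different. The waitlist group's change at 15-18 months is within-patient, so stable clinic differences cancel. It also coincides with follow-up time, so reading it as a PLUS effect needs a common-trend assumption, which is not stated.

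**3. How much could one omitted covariate matter?** Document inputs: 174 enrolled; enrolment 26 March 2015 to 16 March 2017. Assumptions: equal accrual (174/3 = 58 per site) and uniform accrual over time. The waitlist window is 586 days and the later window 136, so Site 3 splits as 58 × 586/722 = 47.1 waitlist and 58 × 136/722 = 10.9 immediate.

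*Power of the baseline ANOVA.* Suppose one cell of size n is shifted by d SD. The noncentrality is d² × n × (174 − n)/174, with F(3, 170) at 5%. For d = 0.4 in the waitlist cell this is 0.16 × 47.1 × 126.9/174 = 5.49.

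| Shift (SD) | Waitlist cell | Site 3 immediate cell |
|---|---|---|
| 0.3 | 28% | 11% |
| 0.4 | 47% | 16% |
| 0.5 | 68% | 23% |

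Under these splits a non-significant test is weak evidence of balance.

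*Residual bias.* Let r be the covariate-outcome correlation and ρ the correlation between outcome measurements, assumed 0.4 to 0.7. With a 0.4 SD imbalance, the bias left after baseline adjustment is 0.4 × r × (1 − ρ).

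*Error rate, Site 1 (or 2) vs waitlist.* The SE in SD units is √(1/58 + 1/47.1) = 0.196. Under compound symmetry, the residual SD of the mean of four follow-ups given baseline is √((1 + 3ρ)/4 − ρ²) = 0.624 (ρ = 0.4) or 0.534 (ρ = 0.7). The error rate is P(|Z + bias/(0.196 × residual SD)| > 1.96).

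| r | ρ | Bias (SD) | Error rate |
|---|---|---|---|
| 0.1 | 0.7 | 0.012 | 5.2% |
| 0.2 | 0.4 | 0.048 | 6.8% |
| 0.3 | 0.7 | 0.036 | 6.4% |
| 0.5 | 0.4 | 0.120 | 16.5% |

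*Unequal accrual.* Let Site 3 enrol 40 to 70 of the 174, with 10% to 50% of them late and the rest shared equally by Sites 1 and 2. The SE then runs from √(1/52 + 1/63) = 0.187 to √(1/67 + 1/20) = 0.255. The same formula gives 5.1-6.9% for r of 0.1-0.2 and 5.8-17.6% for r of 0.3-0.5.

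**The case against.** The strongest reply is that the design is disclosed. Trial Design gives the allocation, the switch date and its reason, and the model term is openly named as clinic and condition combined. A reader might infer that the study presents itself throughout as a randomised trial. The documents do not support that: the error is one clause, and the plan draws no stated conclusion from the tests. This limits the charge, but the clause is still wrong.

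Second, a reader might infer that omitting the covariates is shown to inflate false positives to 17%. It is not shown. That figure needs a 0.4 SD imbalance, correlations up to 0.5 and assumed cell sizes, none of which the documents give. At correlations of 0.1-0.2 the inflation is slight. Equal, uniform accrual also sits poorly with the stated accrual trouble at Site 3, although varying it changes the range little. The calculation concerns the mean of follow-ups with complete data. It does not carry over to the planned 3-month intercept, the slopes or the negative binomial DAST model.

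Third, matching partly covers age group and race/ethnicity in the viral load and CD4 comparisons with Site 4. That stands. But the matching was as close as could be achieved, and it was to enrolled patients overall, so it does not balance Sites 1-3 against each other.

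Fourth, adding a period term and a substance-misuse check may need dates or indicators that the extracted dataset is not confirmed to hold. That also stands, so both are optional below.

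**Conclusion.** The point holds on the text. The randomisation clause contradicts the stated design and should be corrected. Between-group contrasts estimate PLUS plus any clinic difference or, within Site 3, PLUS plus any period difference. Three characteristics that the plan itself treats as possible confounders are unadjusted without a reason, and this matters most for contrasts among Sites 1-3.

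The size of the covariate bias is illustrative only: from almost none to about 0.12 SD under the assumptions above, with error rates of about 5-7% or 6-17% depending on the correlation. The case for adjusting does not rest on the upper figure. It rests on the variables being already collected and cheap to include. Nor should adjustment be read as a cure, since it leaves other clinic and period differences in place.

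**What to change.** 1. In the Data Analysis Plan, replace the randomisation clause with: *Allocation was not randomised (by clinic and, at Site 3, by enrolment date); baseline differences across the site/conditions are described with standardised mean differences.*
2. Adjust all outcome models for age and race/ethnicity, and the self-report models also for education, whatever the baseline p-values. Collapse sparse categories.
3. State that covariates cannot remove clinic or period confounding and that reading Slope 2 as a PLUS effect needs a common-trend assumption. Limit the causal claim accordingly.

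Optional: (a) a sensitivity model adding enrolment period (before or from 1 November 2016), if Sites 1 and 2 enrolled in both periods and, for Site 4, the date of the qualifying viral load was kept. It assumes a period effect shared across clinics and would be imprecise. (b) Substance misuse in the Site 4 match check, if the indicator is available.

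Cost: items 1 to 3 need wording and a few parameters, with no new data. With the five race/ethnicity groups used for matching, age and race/ethnicity add 1 + 4 = 5 parameters per growth factor, against N = 174 for self-report outcomes and 174 + 120 = 294 for viral load and CD4. Education adds its number of categories minus one. The conclusions become more cautious.

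### Omnibus difference tests on 174 patients in four non-randomised site/conditions cannot support baseline equivalence, and age, race/ethnicity, education and the other outcomes' baseline values are tested but not listed as covariates

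*Combined protocol and SAP*

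**What the plan says.** The Trial Design section describes a non-randomised study: "Four sites were distributed across three study conditions in a quasi-experimental design". Sites 1 and 2 gave immediate treatment. Site 3 changed condition over time: "Site 3 implemented both the waitlist condition (Condition 2) from March 26, 2015 to October 31, 2016, and an immediate condition". The four enrolled cells are therefore Site 1, Site 2, Site 3 waitlist and Site 3 immediate.

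The Data Analysis Plan introduces the baseline check with the words "To assess the effectiveness of our randomization procedure", which does not fit that design. The check itself reads: "we used chi-square tests and ANOVAs to investigate the equivalence of possible cofounders across each of the PLUS-enrolled four site/conditions at baseline". Categorical characteristics (race and ethnicity, sexual and gender identity, education) are compared as proportions. Continuous variables are compared as "mean differences across age and baseline outcome values (alcohol severity, drug use severity, medication adherence, viral load, and CD4"). For sparse tables, "we utilized a Fisher's exact test, at" p < .05; that is the only threshold given.

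The outcome models adjust for the baseline score of the same outcome. The adherence, AUDIT and DAST models add gender identity and sexual orientation. The viral load and CD4 models add gender only. Age, race/ethnicity, education and the baseline values of the other outcomes are tested but do not appear as covariates. Clinic and condition enter as one dummy-coded four-category predictor. In the viral load and CD4 models the EMR cohort is an additional subgroup and the referent.

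**The concern.** When condition follows clinic and calendar time, systematic baseline differences are plausible. Eligibility was also widened to drug use in a later amendment, whose date is not given. Among enrolled patients this check is the only stated look at baseline imbalance. A difference test can give evidence of a difference, but its failure to reject is not evidence of equivalence unless the test had high power against imbalances that matter. Two features hold power down here: the total is only 174, and each test is an omnibus across four cells, with 3 degrees of freedom for an ANOVA or a binary characteristic.

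At stake is residual confounding of the condition effects by variables that were collected, were examined in this way, and are not in the models.

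**Working it through.** The documents give no power figure, margin or cell size, so there is no figure of the plan's own to reproduce.

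**Inputs**
- From the Data Analysis Plan: N = 174 enrolled, four cells, so the ANOVA has 3 and 170 degrees of freedom.
- Alpha = 0.05. The plan states this only beside Fisher's exact test; it is assumed for the other tests.
- Assumed: waitlist size n between 20 and 60 (equal cells would be 174/4 = 43.5), with n = 87 as the most favourable split.
- Assumed: waitlist mean shifted by d = 0.5 SD (or 0.25 SD), with the other three cells sharing a mean.

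**Continuous variables (ANOVA)**

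Non-centrality λ = d² × n × (174 − n) / 174, however the other three cells are split. The miss rate is the probability that a non-central F(3, 170, λ) falls below the 5% critical value, 2.66. With equal cells and d = 0.5, λ = 0.25 × 43.5 × 130.5 / 174 = 8.16.

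| Waitlist n | λ, d = 0.5 | Miss rate, 0.5 SD | Miss rate, 0.25 SD |
|---|---|---|---|
| 20 | 4.43 | 61% | 88% |
| 25 | 5.35 | 54% | 86% |
| 30 | 6.21 | 48% | 85% |
| 43.5 (equal) | 8.16 | 35% | 81% |
| 60 | 9.83 | 26% | 78% |
| 87 (best) | 10.88 | 21% | 75% |

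Simulation with 6,000 runs per size agrees: 61% at n = 20, 48% at 30, 34% at 44 and 26% at 60. The shift detectable with 80% power is 0.79 SD at n = 20, 0.58 SD with equal cells and 0.53 SD at n = 60.

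The omnibus form accounts for part of this. A 1-df comparison of waitlist with the rest would miss 0.5 SD 37% of the time at n = 25 and 12% at n = 60, against 54% and 26% above.

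**Categorical variables (chi-square)**

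Take a binary characteristic present in 50% of the waitlist cell and 30% elsewhere. With pooled proportion p, λ = n(174 − n)/174 × 0.20² / [p(1 − p)], on 3 df. With equal cells, p = 0.35 and λ = 32.625 × 0.04 / 0.2275 = 5.74, so the miss rate is 50%. It is 65% at n = 25 and 43% at n = 60.

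**Could any equivalence margin be met?**

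The approximate 95% half-width of a standardised difference is 1.96 × √(1/a + 1/b) for groups of size a and b.
- Best possible split, 87 versus 87: 1.96 × 0.152 = 0.30 SD.
- One cell versus another at equal size, 43.5 each: 1.96 × 0.214 = 0.42 SD.

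So no split of 174 patients could show equivalence within 0.25 SD at 95% confidence. A pass/fail margin would be no cure.

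**Which tested variables remain exposed**

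| Variable tested at baseline | Already in the model? |
|---|---|
| Outcome's own baseline value | Yes, every model |
| Gender | Yes, every model |
| Sexual orientation | Adherence, AUDIT and DAST only; not in the records of the matched cohort |
| Age, race/ethnicity, education | No |
| Baseline values of other outcomes | No |

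**The case against.** The strongest reply is that the plan only investigates equivalence. It never says that p > .05 means balanced, and it never lets a test result add or drop a covariate. This is correct. A reader might infer that variables are formally declared balanced, or that the screen selects the covariates. The documents support neither: no decision rule is written, and the covariates are stated without reference to any test. Changing the tests alone would therefore leave every outcome estimate unchanged. The effect on estimates runs through the covariate list.

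Much is also already handled. Five of the six continuous variables tested are baseline outcome values, each adjusted for in its own model, and gender is in all models. A reader might take the miss rates as the chance of a biased PLUS effect; that does not follow.

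A third reply is that a four-cell test matches the four-category predictor, and that the plan states no pooled immediate-versus-waitlist contrast. That too is right, so balance should be shown cell by cell rather than only pooled.

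Finally, the waitlist size, the 0.5 SD shift and the equal means elsewhere are assumptions, and spread among the other three cells would raise the omnibus power. The figures are conditional. Under the stated pattern, however, even the best split misses 0.5 SD 21% of the time and 0.25 SD 75% of the time.

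What survives is that the tests cannot carry an equivalence claim, and that several measured potential confounders are left unadjusted.

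**Conclusion.** The concern holds in limited form. Non-significant omnibus tests on these 174 patients cannot support equivalence of the four non-randomised cells. Whichever cell size is assumed, a moderate waitlist shift would be missed often and a 0.25 SD shift usually. This rests on alpha 0.05 and on the one-cell-shifted pattern; the actual cell sizes would fix the figure within the range shown.

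The exposure is confined to age, race/ethnicity, education and the baseline values of the other outcomes. Whether any of these is in fact imbalanced, and how far it would bias a condition effect, cannot be told from the documents. Adjusting for them is a cheap improvement that can change the outcome estimates; the change in how balance is reported is a matter of sound interpretation.

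**What to change.** 1. In the Data Analysis Plan, drop any inference of equivalence from p > .05, and describe the check as a description of baseline differences between non-randomised groups, consistent with the Trial Design section.
2. Report standardised differences with 95% CIs for the waitlist cell versus each immediate cell, including Site 3 immediate versus Site 3 waitlist. Set no pass/fail margin, since none of a useful size could be met.
3. Include age, race/ethnicity, education and the relevant baseline values of the other outcomes as covariates, chosen on subject-matter grounds regardless of p-value, at least in a sensitivity model. Do this where the data exist for all groups in the model. For the matched cohort, the plan names age, race and ethnicity, and gender as the variables available for comparison, so education and the self-report baselines may be usable only in models restricted to enrolled patients.

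The cost is one table and one additional set of models from data already held. The downside is a few more parameters in models of 174 patients, or 174 + 120 = 294 with the EMR cohort.

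### The no-treatment EMR cohort is the referent for viral load and CD4, but its match is checked on three demographics only, so a failed match on substance misuse would be neither seen nor adjusted for

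*Combined protocol and SAP*

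**What the plan says.** VL and CD4 are listed among the primary outcomes (Primary Outcome Measures), and Trial Design names the no-treatment group as their comparator. The Data Analysis Plan enters clinic and condition as four dummy-coded categories. For VL and CD4 it adds the EMR cohort as a further subgroup and makes it the referent.

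The section Selection of No Treatment control patients says the 120 controls were drawn at random "while matching as closely as possible to patients enrolled in the trial on key variables". These variables are age group, race and ethnicity, gender, and indicators of substance misuse. The misuse indicators cover documented alcohol abuse or dependence, a substance use diagnosis, "or any indication of substance misuse during the study period".

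The Data Analysis Plan then sets two different baseline checks:

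- **The four PLUS-enrolled site/conditions** are compared on demographics and on "mean differences across age and baseline outcome values (alcohol severity, drug use severity, medication adherence, viral load, and CD4").
- **The control cohort's match** "was assessed by bivariate comparisons with the entire PLUS-enrolled sample" (N = 174), and only "on the available variables of age, race and ethnicity, and gender".

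The VL and CD4 models adjust for the baseline value of the same outcome and for gender. No misuse term is listed.

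**The concern.** The group against which every VL and CD4 coefficient is read gets the weakest comparability check. The plan verifies three of the four matching variables and leaves out misuse, the one closest to the condition the trial treats. It explains the short list by availability, which its own account of the extracted data contradicts.

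Trial Design describes the study as quasi-experimental, so comparability has to be shown. If the control cohort contains more or less misuse than the PLUS sample, and misuse is related to later VL or CD4 beyond the baseline value, part of an apparent difference from no treatment would reflect case mix. Neither the planned check nor the planned model would reveal this.

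**Working it through.** The plan gives no figure to reproduce here. The check is a comparison of passages, followed by an illustration of size.

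**1. Were only three variables available?**

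- *Misuse.* It was used to select the controls, so some indicator existed for them at that stage.
- *HIV outcomes and substance use diagnoses.* The selection section states: "A de-identified dataset was generated linking all patient EMRs to an unique study ID number with the following variables". The list that follows includes HIV clinical outcomes and substance use disorders.
- *Baseline VL and CD4.* The models adjust for baseline on the corresponding outcome and include the controls, so control baseline values must exist.

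The description of three available variables therefore conflicts with the selection section and with the models themselves. The one covariate limit the plan explains is that sexual identity was absent from the controls' records. That reason does not extend to misuse, VL or CD4.

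**2. Does matching make the check unnecessary?** No. It was done as closely as possible, which does not guarantee balance, and no tolerance or achieved balance on misuse is given.

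**3. How large could the effect be?** The documents give neither the effect of misuse on VL or CD4 nor the achieved imbalance, so both are assumed.

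Shift in a contrast = imbalance in misuse prevalence × effect of misuse on the outcome after baseline adjustment (SD units):

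| Imbalance | Effect 0.1 SD | Effect 0.5 SD |
|---|---|---|
| 10 points | 0.10 × 0.1 = 0.01 SD | 0.10 × 0.5 = 0.05 SD |
| 30 points | 0.30 × 0.1 = 0.03 SD | 0.30 × 0.5 = 0.15 SD |

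Unadjusted standard error of one category of size n against 120 controls = √(1/120 + 1/n). Category sizes are not given.

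- Equal sizes, n = 174/4 = 43.5: √(1/120 + 1/43.5) = 0.177 SD
- n = 80: 0.144 SD
- n = 20: 0.242 SD

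The largest shift in the table is 0.15/0.177 = 0.85 of a standard error with equal categories. The smallest is 0.01/0.177 = 0.06.

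**4. Would significance tests be enough for an extended check?** With 120 against 174 and two-sided α = 0.05 (sidedness assumed), the standardised difference detectable with 80% power is (1.960 + 0.842) × √(1/120 + 1/174) = 2.802 × 0.1187 = 0.33 SD. A misuse prevalence of 50% against 60% (assumed) would be detected with about 40% power. A non-significant test would say little, so standardised differences are the better summary.

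**The case against.** The strongest reply is that both problems are already handled. Baseline VL or CD4 is in the model, so a balance table for it describes the groups without changing the estimate. Misuse was dealt with by matching, and checking against the pooled 174 fits a cohort matched to enrolled patients as a whole. The first part largely stands: the gap for VL and CD4 is mainly one of showing comparability. The second stands only if the match on misuse worked, which is what goes unreported.

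A second reply is that a misuse covariate may mislead. Every participant met a self-reported drinking or drug-use criterion at entry, while control misuse is known only from records. A participant without documented misuse is still a user; a control without it may not be. This is a fair limit, but it applies equally to the planned matching. It argues for showing results with and without the term.

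Several stronger readings are tempting, and the documents do not support them:

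- *That the VL and CD4 contrasts are biased.* No imbalance is reported. Aim 4 only plans to compare outcomes by alcohol diagnosis; it is not evidence of an effect, least of all after conditioning on baseline.
- *That having fewer controls than participants leaves some participants without a control.* This presumes one-to-one pairs. The text describes no pairs, and the analysis compares groups.
- *That the excluded records without a return visit should be restored.* This would mean departing from the matched draw, and patients with no follow-up visits would probably add little to a model starting at month 3.
- *That control time zero is wrong.* No index date is stated, but extraction is said to parallel that for participants. This is mainly missing detail.
- *That dated, pre-baseline misuse is already in hand.* The variable list mentions no dates.

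**Conclusion.** The concern holds as a gap in verification and adjustment. The referent for two primary outcomes is checked on age, race and ethnicity, and gender alone, although misuse, baseline VL and baseline CD4 could also be compared. A failed match on misuse would be neither visible nor adjusted for.

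The size and direction of any bias are unknown. Under the assumed ranges the shift is minor if matching worked and approaches one standard error only if it failed badly and misuse has a large effect; the planned check cannot tell these cases apart. The conclusion that the check is incomplete does not depend on those assumptions.

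Contrasts between immediate PLUS and waitlist do not rest on this cohort. Because all controls come from one separate clinic, clinic and control status cannot be separated, and nothing proposed here changes that.

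**What to change.** - **(a) Extend the match assessment** to the EMR misuse indicator used for matching, baseline VL and baseline CD4. Report standardised differences between controls and the PLUS sample, and by site/condition where numbers allow. Correct the statement about which variables were available.
- **(b) Report the VL and CD4 models with and without that misuse indicator**, alongside own baseline and gender. Restrict the indicator to records on or before baseline if dates can be obtained. Note that EMR misuse is an imperfect common measure, because all participants qualified on self-report.
- **(c) State the index date** that defines baseline and the follow-up times for controls, and say what the study period means in the misuse definition.
- **(d) State as a limitation** that clinic and control status cannot be separated.

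The cost is a little extra analysis, a slight loss of precision from the added covariate, and possibly a further extraction to obtain diagnosis dates. No new matching or patient contact is needed.
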